10.2.3 NON-TARGET LESIONS

Any other measurable and abnormal nodal lesions not selected for quantitation as target lesions may be considered non-target lesions. In addition, non-measurable evidence of CLL such as nodal lesions with both diameters <1.0 cm, extra-nodal lesions, bone lesions, leptomeningeal disease, ascites, pleural or pericardial effusions, lymphangitis of the skin or lung, abdominal masses that are not confirmed and followed by imaging techniques, cystic lesions, previously irradiated lesions, and lesions with artifacts may be considered as non-target disease.

The presence or absence of non-target disease should be recorded at baseline and as per the study assessment schedule. If present at baseline, up to 6 non-target lesions should be recorded. The non-target disease at baseline will be used as a general reference to further characterize regression or progression of CLL during assessments of the objective tumor response during treatment. Measurements are not required, and these lesions should be followed as "present" or "absent".

10.3 DEFINITIONS OF TUMOR RESPONSE AND PROGRESSION

Responses will be categorized by the treating investigator as CR, PR, SD, or PD. In addition, a response category of not evaluable (NE) is provided for situations in which there is inadequate information to otherwise categorize response status.

The best overall response will be determined. The best overall response is the best response recorded from the start of treatment until disease/recurrence progression (taking as a reference for disease progression the smallest measurements recorded since treatment started). Where imaging data are available, these data will supersede physical examination data in determining tumor status.

10.4 COMPLETE RESPONSE

To satisfy criteria for a CR, all of the following criteria must be met:

- No evidence of new disease
- ALC in peripheral blood of $<4 \times 10^9/L$
- Regression of all target nodal masses to normal size ≤ 1.5 cm in the LD
- Normal spleen and liver size

- Regression to normal of all nodal non-target disease and disappearance of all detectable non-nodal, non-target disease
- Peripheral blood counts meeting all of the following criteria:
 - ANC $>1.5 \times 10^9/L$ without need for exogenous growth factors (e.g., G-CSF)
 - Platelet count $\geq 100 \times 10^9/L$ without need for exogenous growth factors
 - Hemoglobin $\geq 110 \text{ g/L}$ (11.0 g/dL) without red blood cell transfusions or need for exogenous growth factors (e.g., erythropoietin)

Subjects who fulfill all the criteria for a CR but who have a persistent anemia, thrombocytopenia, or neutropenia or a hypocellular bone marrow that is related to prior or ongoing drug toxicity (and not to CLL) will be considered as a CR with incomplete marrow recovery (CRi).

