⁸ For women of childbearing potential: Serum pregnancy test within 3 days prior to Cycle 1/Day 1; Urine pregnancy tests on Day 1 of each treatment cycle +/- 7 days.

¹⁰ Radiology assessment should include a contrasted CT or MRI imaging of neck, chest, abdomen, and pelvis. For initial treatment, scans to be completed within 30 days prior to Cycle 1 / Day 1. All tumor evaluations post baseline assessment should be performed within 14 days of cycles 3, 6, 12, 18 and 24.. Follow up CTs to be done at investigator discretion/ per standard of care. At the time of response assessment, bone marrow to be performed as per standard of care if other criteria for complete remission are met. CR should only be confirmed once by bone marrow assessment at planned tumor assessments.

¹¹ If U-MRD is confirmed, subjects will complete treatment through the end of that 28-day cycle then return for their first TFO at the subsequent Cycle.

***EOS = End of Study** – EOS visit occurs if subject is discontinuing from the study. Please see Section 5.6 Discontinuation from study , which outlines reasons subject must discontinue from study.

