7.4.1 LOCAL LABORATORY ASSESSMENTS

1. Hematologic profile and serum chemistry to include:

Hematologic Profile		
Hematocrit	Neutrophils	Platelet count
Hemoglobin	Lymphocytes	Absolute lymphocyte count
Erythrocyte count	Monocytes	
Leukocyte count	Eosinophils	
Absolute neutrophil count	Basophils	

Serum Chemistry		
Albumin	Creatinine	SGOT [AST]
Alkaline phosphatase	Glucose	SGPT [ALT]
Bicarbonate/CO ₂	LDH	Sodium
BUN	Magnesium	Total bilirubin
Calcium	Phosphorus	Total protein
Chloride	Potassium	Uric acid

2. Serum pregnancy test.
3. Coagulation lab tests to include PT and INR.
4. Beta2-microglobulin
5. Serum virology to include HBsAG, HBc antibody, HCV antibody, and CMV IgG and IgM or CMV by PCR during screening, then CMV by PCR at subsequent timepoints. If HBc antibody is positive the subject must be evaluated for the presence of active HBV DNA by PCR (see Appendix D). If the subject is CMV IgG or IgM positive, the subject must be evaluated for the presence of CMV DNA by PCR.
6. Bone Marrow biopsy and aspiration for subject that meet the criteria for CR as defined by iwCLL Hallek 2018.

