17 APPENDIX A – CLL RESPONSE DEFINITION

Assessment of response will follow the guidelines published by Hallek et al. (2018).

Assessment of response should include a careful physical examination and evaluation of the blood and marrow.

Table 4 - Response definition after treatment for CLL patients

GROUP	PARAMETER	CR	PR	PD	SD
A	Lymph nodes	None \geq 1,5 cm	Decrease \geq 50% (from baseline) ¹⁾	Increase \geq 50% from baseline or from response	Change of -49% to +49%
	Liver and/or spleen size*	Spleen size $<$ 13 cm; liver size normal	Decrease \geq 50% (from baseline)	Increase \geq 50% from baseline or from response	Change of -49% to +49%
	Constitutional symptoms	None	Any	Any	Any
	Circulating lymphocyte count	Normal	Decrease \geq 50% from baseline	Increase \geq 50% over baseline	Change of -49% to +49%
B	Platelet count	\geq 100.000/ μ l	\geq 100.000/ μ l or increase \geq 50% over baseline	Decrease of \geq 50% from baseline secondary to CLL	Change of -49 to +49%
	Hemoglobin	\geq 11,0 g/dl (untransfused and without erythropoietin)	\geq 11 g/dl or increase \geq 50% over baseline	Decrease of \geq 2 g/dl from baseline secondary to CLL	Increase $<$ 11,0 g/dl or $<$ 50% over baseline, or decrease $<$ 2 g/dl
	Marrow	Normocellular, no CLL cells, no B-lymphoid nodules	Presence of CLL cells, or of B-lymphoid nodules, or not done	Increase of CLL cells by \geq 50% on successive biopsies	No change in marrow infiltrate

1) Sum of the products of 6 or less lymph nodes (as evaluated by CT scans and physical exam in clinical trials, or by physical exam in general practice).

CR, complete remission: all of the criteria have to be met; PR, partial remission: for a PR at least 1 of the parameters of group A and 1 parameter of group B need to improve if previously abnormal. If only one parameter of both groups A and B is abnormal prior to therapy, only 1 needs to improve. PD, progressive disease: at least one of the above criteria of group A or group B has to be met; SD, stable disease: all of the above criteria have to be met. Constitutional symptoms alone do not define PD.

*Spleen size is considered normal if $<$ 13 cm. There is not firmly established, international consensus of the size of a normal liver; therefore, liver size should be evaluated by imaging and manual palpation in clinical trials and be recorded according to the definition used in a study protocol.

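### Section 10.4 omits the marrow and symptom criteria that Appendix A requires for CR, and no rule says how a subject without a marrow result counts in the CR rate

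*Combined protocol and SAP*

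**What the plan says.** Section 10.4 introduces its list with "To satisfy criteria for a CR, all of the following criteria must be met". The items are new disease, lymphocyte count, target nodes, spleen and liver size, non-target disease, and three blood counts. Marrow appears only afterwards, in the sentence on CR with incomplete marrow recovery.

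Appendix A is just as strict: "CR, complete remission: all of the criteria have to be met". Its CR column includes a marrow row, "Normocellular, no CLL cells, no B-lymphoid nodules", and requires no constitutional symptoms. In the same marrow row, the PR column reads "Presence of CLL cells, or of B-lymphoid nodules, or not done".

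Three other places deal with marrow. Footnote 10 to the schedule in Section 7.1 asks for "bone marrow to be performed as per standard of care if other criteria for complete remission are met" and adds "CR should only be confirmed once by bone marrow assessment at planned tumor assessments". Footnote 15 in Section 7.3 repeats the substance for re-treatment. Section 7.4.1, item 6, lists "Bone Marrow biopsy and aspiration for subject that meet the criteria for CR as defined by iwCLL Hallek 2018", without mentioning standard of care.

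The treating investigator assigns response (Section 10.3). Section 11.6.1.2.3 defines the CR rate as the percentage achieving CR, with a 95% confidence interval. It does not name a governing definition or give a rule for a missing marrow.

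**The concern.** Two sets of criteria, each described as complete, define the same response category and do not agree. CR rate is a listed efficacy endpoint (Section 3.2), is analysed with confidence intervals, and is named in the re-treatment objective (Section 3.1). With about 28 subjects per cohort, moving one subject changes the rate by 1/28 = 3.6 percentage points. If sites or programmers work from different pages, the reported rate mixes two definitions and a reader cannot tell how many CRs had a clear marrow. All subjects enter with detectable MRD in blood, so residual marrow disease is a realistic possibility.

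**Working it through.** The plan gives no figure to reproduce: no expected CR rate, no expected frequency of marrow sampling, and no test based on CR. The check is therefore a comparison of texts, followed by an illustration of scale.

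**Step 1. Compare the CR items.**

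| Item | Section 10.4 (with 10.2.2) | Appendix A, CR column |
|---|---|---|
| Marrow | Not on the list | Must be normocellular and free of CLL |
| Constitutional symptoms | Not on the list | Must be absent |
| Spleen | Enlarged if above 12 cm | Normal if below 13 cm |
| Neutrophils | Above 1.5 × 10⁹/L without growth factor | No row |
| Nodes | Longest diameter up to and including 1.5 cm | None at 1.5 cm or above |
| Platelets, haemoglobin | 100 × 10⁹/L; 11.0 g/dL | Same thresholds |

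**Step 2. Apply both to one subject.** Take normal nodes, spleen, liver and counts, no symptoms, and no marrow done. Section 10.4: every listed item is met, so CR. Appendix A: the marrow row is not met, so not CR. Separately, a spleen of 12.5 cm fails 10.4 (12.5 > 12) and passes Appendix A (12.5 < 13).

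**Step 3. Look for a tie-breaker.** The footnotes and 7.4.1 show the intention to confirm CR by marrow. None of them changes the 10.4 list or classifies a subject who was not sampled, and Section 11.6.1.2.3 is silent.

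**Step 4. See where a subject who is not CR goes.** Inclusion criterion 2 admits subjects who are already in SD, PR or CR on current therapy. PR under Section 10.5 generally needs at least two improvements from that on-treatment baseline, or nodal improvement in two stated exceptions. A subject who enters with normal nodes, spleen, liver and lymphocyte count, and has no marrow, has none of these improvements to show. If not CR, this subject can also fail PR and fall to SD. ORR counts CR plus PR, so ORR could fall too.

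**Step 5. Illustrate the scale (assumed counts).** Let n = 28, the approximate cohort maximum. Let m be the number meeting the 10.4 list, d the fraction of these with a marrow done, and c the fraction of those marrows that are clear. The 10.4 rate is m/n. The Appendix A rate is x/n, with x = m × d × c rounded to a whole subject. Exact 95% limits are the 0.025 quantile of Beta(x, n − x + 1) and the 0.975 quantile of Beta(x + 1, n − x); the lower limit is 0 when x = 0. With m = 10:

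| Rule and assumption | x/n | Rate | 95% CI |
|---|---|---|---|
| 10.4 list alone | 10/28 | 35.7% | 18.6 to 55.9 |
| Appendix A, d = 1, c = 0.8 | 8/28 | 28.6% | 13.2 to 48.7 |
| Appendix A, d = 0.8, c = 0.8 (6.4, rounded to 6) | 6/28 | 21.4% | 8.3 to 41.0 |
| Appendix A, d = 0.5, c = 0.8 | 4/28 | 14.3% | 4.0 to 32.7 |
| Appendix A, d = 0 | 0/28 | 0% | 0 to 12.3 |

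If all marrows are done and clear, the two definitions agree on the marrow item. With m = 6 or m = 14, the Appendix A rate runs from 0% up to 21.4% or 50.0%.

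**The case against.** The strongest reply is that the protocol, read as a whole, does require marrow confirmation. Footnote 10 speaks of the other CR criteria, which implies that marrow is one of them, and both footnotes refer to CR being confirmed by marrow. Section 7.4.1 lists the biopsy and aspirate without qualification. On this reading 10.4 was simply not aligned. That stands as evidence of intent, and it rules out saying that the protocol never foresaw a marrow. It does not remove the gap: 10.4 still presents a closed list without marrow, and the unsampled subject is still unclassified.

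It is also fair to say that little rests on CR. It is a secondary outcome described with intervals, no hypothesis test uses it, and the response-based end of treatment depends on confirmed U-MRD in blood (Section 5.2). This limits the importance of the point.

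A reader might infer three stronger things, which the documents do not support:

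- **Less marrow testing gives a higher CR rate under 10.4.** A positive marrow does not block CR under 10.4 as listed, so sampled and unsampled subjects are treated alike. The effect appears only if the two definitions are mixed, or if marrow is read into the 10.4 item on non-target disease. The examples of non-target disease in 10.2.3 do not name marrow.
- **ORR cannot change.** Step 4 of the working shows how it can.
- **An unsampled subject is automatically PR.** The marrow entry in the PR column of Appendix A permits PR without a marrow. It does not waive the required improvement in previously abnormal parameters, or the criteria of 10.5.

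**Conclusion.** The inconsistency is established from the text: the same subject can be CR under Section 10.4 and not CR under Appendix A. The spleen limit and the neutrophil item also differ. The CR rate is affected in initial treatment and in re-treatment, and ORR may be. The primary U-MRD rate, measured in peripheral blood, is not. The size is unknown, because the documents give neither a CR rate nor a marrow frequency. The range of 0% to 35.7% in the illustration rests entirely on the assumption that 10 of 28 subjects meet the 10.4 list. It shows sensitivity and is not a forecast. The point should be corrected before the CR rate is analysed, but it does not threaten the main conclusion of the trial.

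**What to change.** Make one CR definition operative:

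- Add the marrow and constitutional-symptom criteria of Appendix A to Section 10.4. Reconcile the spleen limit, the neutrophil item and the node boundary at exactly 1.5 cm, and refer to this definition in Section 11.6.1.2.3.
- State that a subject with marrow not done or positive does not count as CR in the CR rate.
- Report such subjects in a separate category: all non-marrow CR criteria met, marrow not done or positive (the two shown apart). Do not class them as PR by default, because that can contradict 10.5. State a rule for ORR that is consistent with 10.5.
- Beside each CR rate, show how many subjects were eligible for a marrow and how many had one.

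The cost is wording and one extra table line, with no added biopsies. The reported CR rate may be lower. Because marrow stays a matter of local practice, the rate will still depend on it, now in the conservative direction: in the illustration, 80% clear marrows give 8/28 if all 10 are sampled and 4/28 if half are. The sampling count lets the reader see this.

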10.5 PARTIAL RESPONSE

To satisfy criteria for a PR, the following criteria must be met:

- No evidence of new disease
- A change in disease status meeting ≥ 2 of the following criteria, with 2 exceptions in which only 1 criterion is needed: 1) only lymphadenopathy is present at baseline; 2) only lymphadenopathy and lymphocytosis are present at baseline. In these 2 cases, only lymphadenopathy must improve to the extent specified below:
 - In a subject with baseline lymphocytosis (ALC $\geq 4 \times 10^9/L$), a decrease in peripheral blood ALC by $\geq 50\%$ from baseline or a decrease to $< 4 \times 10^9/L$
 - A decrease by $\geq 50\%$ from the baseline in the SPD of the target nodal lesions
 - In a subject with enlargement of the spleen at baseline, a splenomegaly response as defined in Section 10.2.2
 - In a subject with enlargement of the liver at baseline, a hepatomegaly response as defined in Section 10.2.2
 - A decrease by $\geq 50\%$ from baseline in the CLL marrow infiltrate or in B-lymphoid nodules
- No target, splenic, liver, or non-target disease with worsening that meets the criteria for definitive PD
- Peripheral blood counts meeting 1 of the following criteria:
 - ANC $>1.5 \times 10^9/L$ or $>50\%$ increase over baseline without need for exogenous growth factors (e.g., G-CSF)
 - Platelet count $\geq 100 \times 10^9/L$ or $\geq 50\%$ increase over baseline without need for exogenous growth factors
 - Hemoglobin $\geq 110 \text{ g/L}$ (11.0 g/dL) or $\geq 50\%$ increase over baseline without red blood cell transfusions or need for exogenous growth factors (e.g., erythropoietin)

10.6 STABLE DISEASE

To satisfy criteria for SD, the following criteria must be met:

- No evidence of new disease
- There is neither sufficient evidence of tumor shrinkage to qualify for PR nor sufficient evidence of tumor growth to qualify for definitive PD

10.7 DEFINITIVE DISEASE PROGRESSION

The occurrence of any of the following events indicates definitive PD:

- Evidence of any new disease:
 - A new node that measures >1.5 cm in the LD and >1.0 cm in the LPD
 - New or recurrent splenomegaly, with a minimum LVD of 14 cm
 - New or recurrent hepatomegaly, with a minimum LVD of 20 cm
 - Unequivocal reappearance of an extra-nodal lesion that had resolved
 - A new unequivocal extra-nodal lesion of any size
 - *New non-target disease (e.g., effusions, ascites, or other organ abnormalities related to CLL).
- Evidence of worsening of target lesions, spleen or liver, or non-target disease:
 - Increase from the nadir by $\geq 50\%$ from the nadir in the SPD of target lesions
 - Increase from the nadir by $\geq 50\%$ in the LD of an individual node or extra-nodal mass that now has an LD of >1.5 cm and an LPD of > 1.0 cm
 - Splenic progression, defined as an increase in splenic enlargement by $\geq 50\%$ from nadir (with a minimum 2 cm increase and a minimum LVD of 14 cm)
 - Hepatic progression, defined as an increase in hepatic enlargement by $\geq 50\%$ from nadir (with a minimum 2 cm increase and minimum LVD of 20 cm)
 - Unequivocal increase in the size of non-target disease (e.g., effusions, ascites, or other organ abnormalities related to CLL)
 - Transformation to a more aggressive histology (e.g., Richter's syndrome) as established by biopsy (with the date of the biopsy being considered the date of CLL progression if the subject has no earlier objective documentation of CLL progression).
- Decrease in platelet count or hemoglobin that is attributable to CLL, is not attributable to an autoimmune phenomenon, and is confirmed by bone marrow biopsy showing an infiltrate of clonal CLL cells
 - The current platelet count is $<100 \times 10^9/L$ and there has been a decrease by $>50\%$ from the highest on-study platelet count
 - The current hemoglobin is $<110 \text{ g/L (11.0 g/dL)}$ and there has been a decrease by $>20 \text{ g/L (2 g/dL)}$ from the highest on-study hemoglobin

*Isolated new effusions, ascites, or other organ abnormalities are not sufficient evidence alone of PD unless histologically confirmed. Thus, a declaration of PD should not be made if this is the only manifestation of apparently new disease.

If there is uncertainty regarding whether there is true progression, the subject should continue study treatment and remain under close observation. In particular, worsening of constitutional symptoms in the absence of objective evidence of worsening CLL will not be

considered definitive disease progression; in such subjects, both CLL-related and non-CLL-related causes for the constitutional symptoms should be considered.

Worsening of disease during temporary interruption of study treatment (e.g., for intercurrent illness) is not necessarily indicative of resistance to study treatment. In these instances, CT/MRI or other relevant evaluations should be considered in order to document whether definitive disease progression has occurred. If subsequent evaluations suggest that the subject has experienced persistent definitive CLL progression, then the date of progression should be the timepoint at which progression was first objectively documented.

10.8 NON-EVALUABLE

In a subject who does not have evidence of PD, the occurrence of any of the following conditions indicates a response status of NE:

- There are no images or inadequate or missing images
- Images of the liver and spleen are missing at that time point (with the exception that absence of splenic images will not result in an NE designation in a subject known to have undergone splenectomy).

A time-point will be considered to have a response of NE if any target lesion is missing. PD may be assigned at any time point regardless of the extent of missing target or non-target lesions. Missing non-target lesions will not impact the ability to assess for response or disease progression.

10.9 LYMPHOCYTOSIS DURING THERAPY

Upon initiation of umbralisib or ibrutinib (in retreatment), a temporary increase in lymphocyte counts (i.e., $\geq 50\%$ increase from baseline and above absolute lymphocyte count of 5,000/ μ CL) may occur. The onset of isolated lymphocytosis usually occurs during the first few weeks of umbralisib or ibrutinib therapy and usually resolves within three to four months. Subjects with lymphocytosis should be continued on study drug until the occurrence of definitive disease progression (i.e., disease progression that is manifest by worsening CLL-related signs other than lymphocytosis alone), or the occurrence of another reason to discontinue study therapy.

11 STATISTICAL CONSIDERATIONS

11.1 SAMPLE SIZE AND POWER

The study includes two treatment cohorts. Cohort A is comprised of subjects who will receive ibrutinib in combination with ublituximab and umbralisib. Cohort B is comprised of subjects who will receive venetoclax in combination with ublituximab and umbralisib. Cohort C is comprised of subjects who will receive acalabrutinib in combination with ublituximab and umbralisib. The efficacy of the combination therapy will be evaluated separately for the three cohorts.

11.2 ANALYSIS POPULATIONS

Safety population:

The Safety Population will consist of all subjects who receive at least one dose of any study drug. It will be used to evaluate safety.

Intent-to-Treat (ITT) population:

The ITT population will consist of all subjects who receive any study drug. It will be used to evaluate efficacy endpoints. Subjects with detectable MRD at baseline who do not have disease assessment at any post-baseline visits will be considered non-responders.

11.3 PATIENT DEMOGRAPHICS AND BASELINE CHARACTERISTICS

Baseline demographic and clinical characteristics will be summarized as percentages for categorical variables and as mean, standard deviation, median, minimum and maximum for continuous measures.

